| statistical method | Baseline data were analyzed by Chi-square test. Measurement data are expressed as mean SD. Univariate analysis of variance was used to compare the difference between groups at the same time point, the difference at different time points in the group, and the difference before and after between the two groups. $P < 0.05$ was considered statistically significant, and multiple comparisons were performed by Dunnett-t test.   |
| Expected progress  | Clinical cases will be collected from 2023.1.1 to 2024.12.30, and insufficient cases due to shedding will be added from 2025.1.1 to 2025.12.30.  |

List of abbreviations and term definitions

| abbreviation | definition                          |
|---------------------|--|
| CRS-R               | Coma Recovery Scale-Revised                |
| GCS                 | glasgow coma scale                         |
| NIHSS               | National Institutes of Health Stroke Scale |
| FOUR                | Full Outline of Unresponsiveness Scale     |

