## **3.study endpoint**

3.1 Primary endpoint: GCS score.

3.2 Secondary endpoints: CRS-R Scale (Coma Recovery Scale-Revised), EEG(electroencephalograph), BAEP (Brainstem Auditory Evoked Potential), and EFG (Encephalofluctuography).

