## **8. evaluation index**

8.1 Evaluation of effectiveness: Before and after the intervention and at 4 weeks of treatment: GCS score.

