8.1.1 Glasgow Coma Scale (GCS) : 3 to 15 points

Open eyes (E) : 1-4 points; Vocalization (V) : 1-5 points; Exercise (M) :1-6 points.

The consciousness improvement rate of each patient was calculated according to the following formula:

Consciousness improvement rate of each patient = (score after treatment - score before treatment)/score before treatment  $\times 100\%$

Consciousness improvement rate  $\geq 20\%$  is effective,  $15\% \leq$  consciousness improvement rate  $< 20\%$  is effective, good consciousness

Turnover rate  $< 15\%$  is invalid

Efficiency = (obvious + effective)/(obvious + effective + ineffective)  $\times 100\%$

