## **13. statistic analysis**

### **13.1 Sample size determination**

In this study, 1:1 parallel control was used to estimate the sample size according to the group design of two sample rates comparison sample content estimation formula:

$$n = \frac{2 \times (U_\alpha + U_\beta)^2 \times P \times (1-P)}{(P_1 - P_2)^2} \quad P = \frac{(P_1 * n_1 + P_2 * n_2)}{(n_1 + n_2)}$$

Where,  $U_\alpha$  is the first type of error probability  $U$  value,  $U_\beta$  is the second type of error probability, when bilateral  $\alpha=0.05$ , unilateral  $\beta=0.1$ ,  $U_\alpha=1.96$ ,  $U_\beta=1.28$ ,  $P_1$  is the effective rate of the treatment group,  $P_2$  is the effective rate of the control group, and  $P$  is the rate of the two combinations. According to previous research literature,  $P_1$  and  $P_2$  are estimated to be 79.4% and 54.8%, resulting in  $n \approx 76$ , and the minimum sample size of each group is about 76 cases. As shedding cases were not excluded during the study, the shedding rate was 15%. For the successful completion of the experiment, 87 cases were assigned to each group based on various factors, and 174 cases were required to be included in the two groups.

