### **13.3 Statistical method**

The analysis included case distribution, demographic data, baseline analysis and therapeutic effect analysis. Baseline data included sex, age, stroke type, stroke duration, underlying medical history (diabetes, hypertension, heart disease, chronic obstructive pulmonary disease), and history of smoking and alcohol use. Baseline data were tested by chi-square test. The end point data was the score of the State of Consciousness scale, and the measurement data was expressed as mean SD. Univariate analysis of variance was used to compare the difference between groups at the same time point, the difference at different time points in the group, and the difference before and after between the two groups.  $P < 0.05$  was considered statistically significant, and multiple comparisons were performed by Dunnett-t test.

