### **13.4 Statistical software and general requirements:**

- 1)All statistical analysis was performed using SPSS25.0 statistical software.
- 2)Measurement data were described using mean, standard deviation, median, maximum and minimum values.
- 3)Counting data are described by frequency and percentage.
- 4)All data in the experiment were tested for normality.
- 5)Baseline data were analyzed using Chi-square test. Measurement data are expressed as mean SD. Univariate analysis of variance was used to compare the difference between groups at the same time point, the difference at different time points in the group, and the difference before and after between the two groups.  $P < 0.05$  was considered statistically significant, and multiple comparisons were

performed by Dunnett-t test.

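### The trial is sized on a difference in effective rate, but the plan compares mean scores at every visit, names no test of the rate and designates no primary visit

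*Combined protocol and SAP*

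**What the plan says.** **Sample size.** Section 13.1 and the summary use the formula for comparing two proportions, with two-sided alpha 0.05 and beta 0.1. P1 "is the effective rate of the treatment group", set at 79.4% against 54.8% in the control group. The result is about 76 per group, raised to 87 per group (174 in total) for 15% dropout.

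**Endpoint.** Section 3.1 reads "Primary endpoint: GCS score", with no visit and no form (score, change or rate). Section 8.1 reads "Before and after the intervention and at 4 weeks of treatment: GCS score". Section 8.1.1 defines a GCS responder rate, "Efficiency = (obvious + effective)/(obvious + effective + ineffective", and section 8.1.2 defines a second responder rule on CRS-R. Section 13.1 does not say which rule or which visit its two rates refer to.

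**Analysis.** Section 13.3 states: "The end point data was the score of the State of Consciousness scale, and the measurement data was expressed as mean SD". The test is given as "Univariate analysis of variance was used to compare the difference between groups at the same time point", and the same method is used within groups over time and for the before-after difference between groups. Chi-square appears only for baseline: "Baseline data were analyzed by Chi-square test" (summary, repeated in 13.3 and 13.4). For categorical data, section 13.4 says "Counting data are described by frequency and percentage". The threshold is P<0.05 throughout, with Dunnett-t for multiple comparisons that are not named.

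**The concern.** The quantity that fixes the sample size is binary, and the quantity tested is a mean. The 90% power is a property of a two-proportion test that the plan never says it will run. For the ANOVA that it does plan, the documents give neither a GCS difference nor an SD, so its power cannot be worked out and a null result could not be judged against a known power.

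The primary endpoint also leaves both the visit and the form of the outcome open. GCS is scored at weeks 1, 2, 3 and 4 and again four weeks after discharge, and between-group comparisons are planned at each time point and on change. Whichever comparison falls below 0.05 could be presented as the primary result. The main objective in section 2.1 is confirmatory, so this bears on the trial's one confirmatory claim.

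**Working it through.** **1. Reproduce the plan's figure.** Inputs from 13.1: U values 1.96 and 1.28, P1 = 0.794, P2 = 0.548, 1:1 allocation.

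- P = (0.794 + 0.548)/2 = 0.671.
- n = 2 × 3.24² × 0.671 × 0.329 / 0.246² = 76.6 per group (plan: about 76).
- Dropout: 76 × 1.15 = 87.4 (plan: 87). Losing 15% of 87 leaves 87 × 0.85 = 74 evaluable.

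The arithmetic is sound. The fault is that the planned analysis does not match it.

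**2. Power of the test the trial was sized for.** For the pooled two-proportion test, power = Φ{[0.246√n − 1.96√(2 × 0.671 × 0.329)] / √(0.794 × 0.206 + 0.548 × 0.452)}.

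- n = 76: 90.5%.
- n = 74: [2.116 − 1.302]/0.641 = 1.269, giving 89.8%.

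**3. What the planned mean comparison can detect.** Only a standardised difference can be given. At 90% power, d = 3.24 × √(2/n).

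- n = 76: 0.526 SD. n = 74: 0.533 SD.
- With ANCOVA on baseline, multiply by √(1 − r²). At n = 74 this gives 0.46 SD for r = 0.5 and 0.38 SD for r = 0.7. Both correlations are assumptions.

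**4. Chance of at least one false positive on GCS.** There are five post-baseline visits (section 7.2 and the flow chart), each tested at 0.05. If the tests were independent, 1 − 0.95⁵ = 22.6%. Scores from one patient are correlated, so the error was simulated (1,000,000 draws, no true effect, equal correlation ρ across baseline and the five visits). The values of ρ are assumptions.

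| Tests counted | ρ = 0.5 | 0.7 | 0.8 | 0.9 |
|---|---|---|---|---|
| Five visit tests | 18.3% | 14.8% | 12.8% | 10.2% |
| Plus one week-4 change test | 21.8% | 18.8% | 17.0% | 14.6% |
| Plus change tests at all five visits | 30.8% | 29.1% | 27.9% | 26.1% |

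The last row is a worst case: the plan does not say that change is tested at every visit.

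**5. Does Dunnett-t control this?** No. With two arms there is one comparison with control at each visit, so nothing is adjusted across visits. It could serve visits against baseline within a group, but the plan does not say so. The plan is also silent on how repeated scores are handled within a group. Treating them as independent would make the standard errors too large, so that omission adds nothing to the figures above.

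**6. If the sample size is 72.** Section 4 gives 72 patients, not 174. At 36 per arm with no dropout, the rate test has 60.7% power (62.6% by exact binomial calculation), and the mean comparison needs 3.24 × √(2/36) = 0.76 SD for 90% power.

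**The case against.** **The score analysis may well be adequately powered.** If the effective rate is a cut-point on a normally distributed improvement with equal SDs, 79.4% against 54.8% implies a shift of 0.82 − 0.12 = 0.70 SD. A comparison of mean improvement would then have about 99% power at 74 per arm and about 84% at 36. This is a fair warning against calling the trial underpowered, and that is not claimed here. But the plan does not make that assumption, the 8.1.1 rule uses percent change so the mapping is only approximate, and the argument leaves the choice among visits untouched.

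**Section 13.4 does not forbid a test of the rate.** Its line on count data is a descriptive-statistics line, parallel to the one for measurement data. That stands: the accurate statement is that no test of the rate is named anywhere.

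**Section 8.1 mentions week 4.** If only week 4 counted, testing both score and change there would give about 9% to 10% error. But 8.1 also lists before and after the intervention, does not call any time primary, and is not carried into 3.1 or 13.3. Section 7 evaluates effectiveness at all four treatment weeks.

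**The ANCOVA gains are speculative.** Entry is restricted to GCS 3 to 9, which tends to lower the correlation with baseline. That stands; only the 0.53 SD figure is free of this assumption.

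**Other gaps remain.** Under 8.1.1 a one-point gain counts as a response from baseline 6 (16.7%) but not from baseline 7 (14.3%), and neither deaths nor missing week-4 scores are assigned a role in the test. These are real but separate questions.

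**Conclusion.** The concern holds and must be fixed. The 90% power applies to a rate comparison that the plan does not name. The power of the planned ANOVA is unknown from the documents; at 74 to 76 evaluable per arm it reaches 90% only for a difference of about 0.53 SD unadjusted. With no primary visit or form of the endpoint, the false-positive chance on GCS is about 10% to 18% for the five visit tests and 15% to 22% with one week-4 change test. It would reach 26% to 31% only if change were tested at all five visits. These ranges rest on assumed equal correlations of 0.9 to 0.5. The mismatch and the missing primary visit follow from the text alone.

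**What to change.** In sections 3.1, 8.1 and 13.3, designate week 4 of treatment as the single primary time point, with one between-group test at two-sided 0.05. Then choose one of the following.

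- **(a) Rate.** Make the week-4 effective rate under the GCS rule of 8.1.1 primary, tested as a two-proportion comparison and reported as a risk difference with 95% CI. First confirm that 79.4% and 54.8% refer to that rule and not to the CRS-R rule of 8.1.2. If they do, 174 patients give about 90% power.
- **(b) Score.** Make the week-4 GCS score primary, by ANCOVA on baseline GCS. Restate 13.1 with a GCS difference and SD justified as clinically worthwhile. With 174 patients, 90% power corresponds to about 0.53 SD before any gain from baseline adjustment.

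Under either option, reconcile 174 with the 72 in section 4. Analyse the other visits as secondary in one repeated-measures mixed model, state which comparison (if any) Dunnett-t serves, and do not use within-group changes as evidence of efficacy.

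**Cost.** A protocol amendment approved by the Ethics Committee before implementation (sections 14.3 and 15.1), and made before outcome data are seen by arm. Because the schedule runs only to the end of 2025, the sponsor should confirm that this is still possible. No assessments beyond those scheduled and no patients beyond 174 are needed. The price is that results at other visits can no longer be claimed as primary.

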### **5.2 inclusion criteria:**

(1) sign the informed consent voluntarily;

(2) met the above diagnostic criteria, and the GCS score was between 3 and 9 (the score was scored by a rehabilitation physician, and the patient had not used sedatives or anesthetics on the day of the score);

- (3) The patient's condition is stable, vital signs are stable, and the onset time of consciousness disturbance caused by stroke is confirmed to be less than 6 months;
- (4) Cerebral infarction or cerebral hemorrhage confirmed by clinical and auxiliary examination is the only factor causing consciousness disorder, excluding other diseases caused consciousness disorder patients;
- (5) those aged between 18 and 85;
- (6) Family members or authorized principals know and sign informed consent;
- (7) did not enter other clinical studies at the same time.

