### **(2) Evaluation:**

Consciousness levels were assessed before intervention, at 1, 2, 3, and 4 weeks of treatment, and 4 weeks after discharge: GCS score, NIHSS score, CRS-R Scale (Modified Coma Recovery Scale), and FOUR scale score . Electroencephalogram, brainstem auditory evoked potentials and encephalofluctuograph were examined before intervention and at 4 weeks of treatment.

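### GCS is compared between arms only by unadjusted ANOVA of raw and before-after scores, with no baseline GCS covariate and no main comparison named, while the 8.1.1 success rule depends on baseline GCS

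*Combined protocol and SAP*

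**What the plan says.** Section 3 defines the primary endpoint in a few words: "3.1 Primary endpoint: GCS score". It gives no visit and no summary measure. Section 8.1 comes nearest to a main comparison, with "Before and after the intervention and at 4 weeks of treatment: GCS score", but it does not choose between the score, its change and the effective rate.

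Section 13.3 sets out the comparison of arms: "Univariate analysis of variance was used to compare the difference between groups at the same time point", and also "the difference before and after between the two groups". Section 13.4 and the statistical method row of the summary repeat this. No covariate is named in any of the three places.

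Baseline GCS is available for everyone. Section 7.2 states "Consciousness levels were assessed before intervention, at 1, 2, 3, and 4 weeks of treatment, and 4 weeks after discharge: GCS score", and the test flow chart agrees. It is nevertheless absent from the baseline variables listed in 13.3, and section 4.2.1 mentions no stratification by it.

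Section 8.1.1 defines a responder measure as a percentage of baseline: "Consciousness improvement rate of each patient = (score after treatment - score before treatment)/score before treatment". A value of 15% or more counts as effective. Section 13.1 sizes the trial on two effective rates, 79.4% and 54.8%, but section 13.3 names no between-arm test for such a rate. The chi-square test is assigned only to baseline data.

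**The concern.** Three gaps sit together.

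- **No baseline covariate.** A patient's entry GCS will usually predict the later GCS. The same-time-point ANOVA ignores it, and the before-after ANOVA subtracts it with a slope fixed at 1. Which of the two is more precise depends on a correlation and an SD ratio that nobody knows beforehand.
- **No named main comparison.** With both analyses planned and neither designated, either could be put forward as the trial's result.
- **A success rule that shifts with baseline.** A fixed percentage of an integer score requires different gains from different patients, so one overall effective rate mixes unlike successes.

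At stake are efficiency and a clear reading of the result. Allocation is randomised, so an unadjusted comparison fixed in advance is not biased.

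**Working it through.** **The plan's own figure.** Section 13.1 uses n = 2(1.96 + 1.28)² × P(1 − P)/(P1 − P2)², with P1 = 0.794, P2 = 0.548 and P = 0.671. This gives 76.6, against a stated value of about 76 per arm, and 76 × 1.15 = 87.4, against a stated 87. The figure reproduces. It is a calculation for two unadjusted rates and involves no mean GCS score.

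**Success rule.** Section 5.2 requires that "the GCS score was between 3 and 9". The smallest whole-point gain that reaches 15% is 0.15 × baseline, rounded up.

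| Baseline GCS | 1 point as % of baseline | Points needed |
|---|---|---|
| 3 | 33.3 | 1 |
| 4 | 25.0 | 1 |
| 5 | 20.0 | 1 |
| 6 | 16.7 | 1 |
| 7 | 14.3 | 2 |
| 8 | 12.5 | 2 |
| 9 | 11.1 | 2 |

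The required gain doubles between 6 and 7. This step needs no assumption.

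**Precision.** Let ρ be the correlation of baseline with week-4 GCS, and k the baseline SD divided by the week-4 SD. The documents give neither, so both are assumed: ρ = 0.3, 0.5, 0.7 and k = 0.5, 0.6, 0.7, 1. Variance relative to the week-4 score is:

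- same-time-point ANOVA: 1
- before-after ANOVA: 1 + k² − 2ρk
- ANCOVA: 1 − ρ²

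The saving by ANCOVA is therefore ρ² against the first, or 9%, 25% and 49%, whatever k is. Against the second it is (k − ρ)²/(1 + k² − 2ρk):

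| k | ρ = 0.3 | ρ = 0.5 | ρ = 0.7 |
|---|---|---|---|
| 0.5 | 4.2% | 0.0% | 7.3% |
| 0.6 | 9.0% | 1.3% | 1.9% |
| 0.7 | 15.0% | 5.1% | 0.0% |
| 1.0 | 35% | 25% | 15% |

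The smaller of the two savings in each cell is the gain over the better planned ANOVA: 0-9% for k = 0.5-0.7, and 9-25% for k = 1. Between the tabulated correlations it reaches 12%, at k = 0.7 and ρ = 0.35. The larger is the gain over the worse one: 9-49%, and 25-49% for k = 1. At k = 0.7 the raw score is the better choice if ρ = 0.3, and the change if ρ = 0.7.

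A ratio below 1 is likely because entry is confined to 3-9 while the scale is "Glasgow Coma Scale (GCS) : 3 to 15 points". As an illustration only, scores spread evenly over 3-9 and over 3-15 have SDs of 2.0 and 3.74, a ratio of 0.53.

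**Cost of the covariate.** Estimating the slope inflates variance by about 1/(N − 4). That is 1/170 = 0.6% at N = 174, or 1/68 = 1.5% at the 72 patients given in section 4. The savings do not otherwise depend on N.

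**Effect of leaving the choice open.** If significance could be claimed from either the raw or the before-after test at week 4, null simulations with 76 per arm and normal scores give a false-positive chance of about 7-8% for k = 0.5-0.7 and about 9% for equal SDs, against the nominal 5%. Dunnett's test does not help: two arms give one contrast per visit, and it does not adjust across raw score and change.

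**Sampling error of the rate difference.** √(0.794 × 0.206/87 + 0.548 × 0.452/87) = 0.0688, or 6.9 percentage points; at 76 per arm it is 7.4. Chance imbalance in baseline GCS is already inside this standard error. The size and direction of any shift it causes in this trial cannot be derived from the documents.

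**The case against.** The strongest reply is that the missing covariate costs little. Unadjusted tests are valid under randomisation, and the before-after comparison already uses baseline GCS. At the SD ratios argued to be likely, ANCOVA gains only 0-9% over the better planned analysis at the three correlations used, and some cells are no larger than the slope-estimation cost. All of these savings rest on assumed values, and the narrow entry range that lowers k may lower ρ as well. This stands, and it keeps the point one of precision. It does not remove the point, because the better analysis cannot be identified beforehand and the worse one costs 9-49%.

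Second, section 8.1 does point to 4 weeks. That narrows the choice of visit but leaves raw score, change and effective rate open.

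Third, section 13.1 does not cite 8.1.1 for its effective rates, and 8.1.2 contains another responder rule, on CRS-R. The GCS rule is the likelier source because GCS is the primary endpoint, but that is an inference. The step between GCS 6 and 7, and the absence of a named test for the rate, hold either way.

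Fourth, adjustment leaves the percentage rule in place. That is true: the dependence on baseline becomes visible but is not removed.

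**Conclusion.** The concern holds. The text of 13.3, 13.4 and the summary is consistent: unadjusted ANOVAs of the score and of its change, no baseline GCS covariate, and no designated main comparison. The 1-point versus 2-point split in the success rule follows from 8.1.1 and the entry range alone.

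The precision figures rest on the assumed correlations and SD ratios. Under them ANCOVA is never worse than either planned ANOVA, apart from the one degree of freedom spent on the slope, and it removes the need to guess which is better. This is an improvement the sponsor should make; it does not invalidate the trial. The 76 per arm is unaffected as arithmetic for two rates.

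**What to change.** - **Main comparison.** In 13.3, with matching text in 13.4 and the summary, name one main between-group comparison: ANCOVA of week-4 GCS with arm as factor and baseline GCS as covariate. It replaces the two unadjusted ANOVAs for that purpose.
- **Effective rate.** Name one between-arm analysis of the 8.1.1 rate, adjusted for baseline GCS, and report the rate separately for baseline 3-6 and 7-9. Either logistic regression or a Mantel-Haenszel comparison stratified 3-6 versus 7-9 would serve, but one must be fixed in advance. The stratified form follows the step in the rule, which a linear baseline term in a logistic model would not capture.
- **Sample size.** State in 13.1 that 174 was calculated for an unadjusted comparison of effective rates and not for this ANCOVA.

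**Cost.** The change needs a protocol and SAP amendment with ethics approval (section 14.3, on revising the protocol), settled before the database lock described in 12.2. It needs no new data, visits or patients. There are three drawbacks: the adjusted rate is less directly comparable with 79.4% and 54.8%; the main comparison is then not the one on which 174 was calculated; and the percentage rule itself stays.

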## **7. Research methods and procedures**

All subjects need to sign informed consent before screening, and successful subjects can enter this study. According to the protocol, the experimental group and the control group were treated respectively, and the effectiveness and safety were evaluated at 1, 2, 3 and 4 weeks. Telephone and video follow-up were conducted 4 weeks after discharge for statistical analysis. Treatment continued until subjects completed the 4-week course or met any of the exit criteria. Participants are evaluated comprehensively by the investigator, and if it is determined that the continuation of the experimental treatment can bring clinical benefit to the subject, the treatment can be continued until the subject's PD, intolerance, or death.

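### No single primary GCS test is fixed at week 4, and the stated 90% power belongs to an effective rate that section 13 does not test

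*Combined protocol and SAP*

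**What the plan says.** **Endpoint.** The summary (efficiency analysis row) and section 3.1 name the GCS score, with no visit, summary measure or test.

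**Visit.** Section 8.1 lists GCS before and after the intervention and at week 4. The study design row of the summary describes the 4-week assessment as the one after completion of treatment. Section 7 states that "the effectiveness and safety were evaluated at 1, 2, 3 and 4 weeks", and section 7.2 adds an assessment 4 weeks after discharge. No visit is called primary.

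**Analysis.** Section 13.3, repeated in substance in the summary and in section 13.4, says: "The end point data was the score of the State of Consciousness scale". It continues: "Univariate analysis of variance was used to compare the difference between groups at the same time point", followed by "the difference at different time points in the group, and the difference before and after between the two groups". Every result is judged at P<0.05, and "multiple comparisons were performed by Dunnett-t test" without a statement of which comparisons form the family.

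**Effective rate.** Section 8.1.1 defines "Consciousness improvement rate of each patient = (score after treatment - score before treatment)/score before treatment" and counts an improvement of at least 15% as effective. Section 13.1 sizes the trial on effective rates of 79.4% and 54.8%, at two-sided 0.05 and beta 0.1. Section 13 names no test for this rate; chi-square appears only where "Baseline data were tested by chi-square test".

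**The concern.** Two separate things are at stake.

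- **Error rate.** Week-4 score and before-after change from baseline to week 4 are both between-group tests of GCS at P<0.05, and nothing says which one decides the trial. If a significant result on either may be reported as primary, the chance of a false-positive trial is above 5%.
- **Power.** The sample size was computed for a difference in effective rates, while the analysis section treats the score as the end point. The 90% therefore says nothing about the mean-score comparisons that are planned, and the quantity it does describe has no test. This holds even if multiplicity is set aside.

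**Working it through.** **1. Reproduce the sizing (section 13.1).** P = (0.794 + 0.548)/2 = 0.671.

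n = 2 × (1.96 + 1.28)² × 0.671 × 0.329 / 0.246² = 2 × 10.4976 × 0.220759 / 0.060516 = 76.6 (plan: about 76).

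76 × 1.15 = 87.4 (plan: 87). After 15% loss, 87 × 0.85 = 74 evaluable per group. The arithmetic is not the fault.

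**2. What the 90% refers to.** At 74 per group the pooled standard error is √(2 × 0.220759/74) = 0.0772. Then 0.246/0.0772 − 1.96 = 1.22, giving 89% power. Other standard forms give 89.8% (normal approximation) and 90.0% (exact, uncorrected chi-square). So the 90% is right for the effective rate. No GCS standard deviation is given, so no power follows for mean scores.

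**3. Dunnett.** With one active arm and one control there is a single comparison per visit, and the Dunnett critical value is that of the two-sample t-test. Nothing is adjusted between score and change, or across visits.

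**4. Score or change at week 4.** Assume equal SDs and baseline-to-week-4 correlation ρ. The two test statistics then correlate at √((1 − ρ)/2). The chance under the null that at least one exceeds ±1.96 is:

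| ρ | correlation of tests | either significant |
|---|---|---|
| 0.3 | 0.592 | 8.8% |
| 0.5 | 0.500 | 9.1% |
| 0.8 | 0.316 | 9.5% |

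Null simulation with whole-number GCS gives 8.4-8.9% for ρ from 0.3 to 0.8. The range is therefore about 8-9.5%.

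**5. Adding the effective rate at week 4.** Assumed: baseline mean 6, SD 1.7, limited to 3-9; mean week-4 gain 1.2; follow-up SD 2.0, limited to 3-15; effective means a gain of at least 15%; uncorrected two-proportion test; 74 per group. The simulated effective rate is 55-59%, close to the plan's 54.8%. The chance that at least one of the three tests is significant is 11.6-12.2%. Two other assumed distributions give 11.0-12.4%, and 36 per group gives 10.9-11.7%.

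**6. Recruitment total.** Section 13.1 requires 174 patients; section 4 gives 72. At 36 per group, power for the effective rate is 60-63%. After 15% loss (36 × 0.85 = 30.6, taken as 31) it is about 54-55%.

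**7. Detectable difference if the score is primary.** For ANCOVA at 74 per group and 90% power, the difference in SD units is (1.96 + 1.28) × √(2(1 − ρ²)/74) = 0.508, 0.461 and 0.380 at ρ = 0.3, 0.5 and 0.7. With t quantiles these become 0.512, 0.465 and 0.383.

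**8. Secondary: within-group comparison over time.** Univariate ANOVA across visits names no patient term. Read as written, it treats repeated scores from one patient as independent. With equal correlation between visits, the standard error of a time difference is too large by 1/√(1 − ρ), or 1.41 to 2.24 for ρ = 0.5 to 0.8. With correlation that decays over time (one-week correlation 0.5 to 0.8), the factor from baseline to week 4 is 1.03 to 1.30.

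**The case against.** **Week 4 is plainly intended.** Section 8.1 is the effectiveness section and names week 4 for GCS. The summary equates four weeks of treatment with completion, which gives a natural meaning to the score after treatment in section 8.1.1. Sections 7 and 7.2 are assessment schedules. This largely stands, and the point is therefore argued at week 4. What remains is that no sentence makes week 4 primary, and that fixing it still leaves score and change unranked.

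**The effective rate is not a planned test.** This also stands. Section 13 gives it no test and calls the score the end point. The error rate for the planned tests is therefore the 8-9.5% figure; 11-12% applies only if the rate may be claimed as well. The objection confirms the power mismatch.

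**The simulation inputs are assumed.** True, but the week-4 figures barely move across the correlations, distributions and group sizes tried, and the power mismatch needs no simulation.

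**Stronger readings that a reader might infer.**

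- That a significant result at any visit counts, which would raise the error rate well above these figures. No passage says so.
- That treating repeated scores as independent distorts the treatment comparison. It does not: it affects only the within-group comparison over time, and makes that conservative.

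**Conclusion.** The point holds in a limited form. The likely visit is week 4, but it is not designated. At that visit the plan leaves two unranked between-group tests of GCS at P<0.05, and Dunnett-t does not adjust across them. The stated 90% power belongs to a third quantity that the analysis section does not test.

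The false-positive chance is about 8-9.5% if either planned test may be claimed, and about 11-12% if the effective rate may be claimed too. Both figures are conditional on such a choice being made, and on the assumed correlation (0.3-0.8) and GCS distribution. The power mismatch depends on neither. This should be corrected before unblinding; it does not invalidate the design.

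**What to change.** Before unblinding, name week 4 as the primary visit, define the post-treatment score in section 8.1.1 as the week-4 score, and fix one primary test at two-sided 0.05. The sponsor chooses:

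- **Option 1: week-4 GCS by ANCOVA**, with group as factor and baseline GCS as covariate. State that the 90% in section 13.1 was computed for effective rates and does not carry over. Give instead the detectable difference: 0.51, 0.47 or 0.38 SD at 74 per group for baseline correlation 0.3, 0.5 or 0.7. The sponsor must supply a GCS SD to express this in points.
- **Option 2: week-4 effective rate by a named two-proportion test**, with the difference and its 95% CI. This keeps the sizing basis (89-90% power at 74 per group).

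Under either option:

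- Make the other contrasts, the other visits and CRS-R secondary.
- Name the primary analysis set. The summary's full analysis set asks for one intervention and a baseline measurement; section 13.2 asks for one treatment and one effectiveness evaluation. Neither guarantees a week-4 score, so state how a missing one is handled.
- Reconcile 174 patients (section 13.1) with 72 (section 4), because every power figure depends on it.
- As a secondary matter, analyse scores over time with a repeated-measures mixed model in place of univariate ANOVA across visits.

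**Cost.** SAP wording and, under option 1, a new power statement; no new data or software. Other visits and contrasts can no longer count as primary. Option 1 may lower the stated power. Option 2 reduces the score to yes/no: a 1-point gain is effective from baseline 6 (1/6 = 16.7%) but not from 7 (1/7 = 14.3%). If the test chosen under option 2 is the uncorrected chi-square, it can run slightly above 5%, at about 5.3-5.8% with 74 per group.
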